8.2 Statistical Analysis

The clinical trial will be reported according to the CONSORT guidelines for clinical trials. Baseline data (sex, age, diagnosis distributions etc.) will be presented in tabular form. Data will be summarised using descriptive statistics. Data will be analysed according to intention-to-treat criteria. A secondary analysis will be an on-treatment analysis. A secondary analysis will be by baseline mean nocturnal oxygen saturation. Whilst patients may, of course, withdraw from treatment at any time, they will all be encouraged to remain under follow up.

Statistical comparisons will compare the measurements of primary and secondary outcomes between the groups. For continuous data, ANCOVA will be used to compare the groups, whilst controlling for the baseline measure and confounding factors. KM and Cox regression will be used for time to event data such as mortality. All analyses will be undertaken on SPSS.

Missing data is a well recognised problem in longitudinal studies, particularly with patients with advanced disease. We will handle missing data by using the extreme values. By making the assumption that the missing value is the worst it could be for the intervention and the best it could be for the standard care group (best medical therapy). If there remains a statistically significant difference between treatments then one can be sure that the results are robust. Other techniques that we have considered involve building a regression equation to predict the value of the missing data from the baseline characteristics from patients with no missing values or the use of other imputation techniques such as mean values. Expert statistical advice will be provided by [name].

9. Pharmacovigilance

The collection and reporting of data on adverse events and serious adverse events will be in accordance with ICH GCP and the Research Governance Framework 2005.

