[name], Director of York Trials Unit, [name]. [contact], [contact], [contact]

Contents

1. Trial Synopsis	3
2. Background and Rationale	5
3. Aims and Objectives	7
4. Study Design	9
5. Patient Eligibility and Participation	.13
6. Trial Evaluations	16
7. Health Economic Assessment	22
8. Statistical Considerations	23
9. Pharmacovigilance	24
10. Research Governance	27
11. Ethics, Confidentiality and Liability	. 30
12. The Study Team	31
Deferences	21

1. Trial Synopsis

Patients with Chronic Heart Failure (CHF) commonly have significant limiting symptoms despite optimal management. The prevalence and clinical relevance of hypoxaemia in patients with CHF is incompletely understood. Currently, Home Oxygen Therapy (HOT), in various forms, is used commonly despite the absence of evidence of benefit.

The present study seeks to address the uncertainties surrounding home oxygen therapy for patients with chronic heart failure who are still severely symptomatic despite maximally tolerated medical therapy. The study will randomise 450 patients equally to its active treatment arms. These are (a) best medical therapy without oxygen (b) best medical therapy with daytime Long Term Oxygen Therapy (LTOT for at least 15 hours per day in the home, including overnight hours) or (c) best medical therapy with Nocturnal Oxygen Therapy (NOT overnight in the home). Each patient will remain within the study for at least 1 year. All patients will continue active treatment within the study until the last patient recruited has completed their 1 year's active treatment, meaning that the first patient recruited will remain on active treatment for approximately 2 years in total. Patients can withdraw at any point, and such incidences will be included within the quality of life analysis.

Primary Research Question

Is there a quality of life benefit from home oxygen therapy given as either long term daytime or nocturnal oxygen therapy compared with best medical therapy in patients with stable severely symptomatic chronic heart failure?

Primary Objectives

 To assess the quality of life benefits of home oxygen therapy in the management of patients with stable CHF who are still severely symptomatic despite maximally tolerated medical therapy.

Secondary Objectives

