6.2 Quality of Life Questionnaires & Assessments

The quality of life assessments undertaken are:

Minnesota Living with Heart Failure questionnaire (MLWHF)

This is a validated, disease specific, QoL instrument widely used in heart failure research both to assess symptoms severity and response to treatment.²⁵ ²⁶ It is the primary endpoint measure for the present study. It consists of 21 questions focussing on the impact of heart failure on QoL. Patients are asked to rate the extent to which their heart failure has prevented them from living as they wanted during the last month using questions rated on a scale of 0 (no effect) to 5 (very much). The questionnaire is scored by summating the responses to all 21 questions; thus resulting in a score from 0 to 105 with a higher score reflecting poorer quality of life. The MLWHF validated Quality of Life (QoL) score version 2 is easy to complete and has been shown to be especially effective in older patients with co-morbidities.²⁷

• The EuroQoL EQ-5D

This is a self-administered, validated, measure of health status and consists of a 5-question multi-attribute questionnaire and a visual analogue self-rating scale.²⁸ Pespondents are asked to rate severity of their current problems (level 1= no problems, level 2 = some/moderate problems, level 3 = severe/ extreme problems) for five dimensions of health: mobility, self-care, usual activities, pain/discomfort, and anxiety/depression. Patients can be classified into 243 (3⁵) health states plus two further additional states (unconscious and dead).

• Epworth Sleep Score

The Epworth is a standard scale for screening for, and assessing the severity of, sleep disordered breathing.

Breathlessness Numerical Rating Scale

This measures average and worst breathlessness and distress due to breathlessness over the past 24 hours (anchored with "not breathless" and "worst breathlessness imaginable").³⁰ It is highly correlated with VAS scores and more repeatable.³¹ It will also used to assess patients satisfaction with oxygen treatment (anchored with "not at all satisfied" to "very satisfied").

Hospital Anxiety and Depression Scale

The HAD score is a well validated screening tool for depression and anxiety and easy to complete.³²

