8.1 Sample Size

Study power is difficult to calculate. The Minnesota Living with Heart Failure scale is the most widespread tool for assessing quality of life in patients with chronic heart failure. An improvement of 5 is sometimes taken to be a minimum clinically important difference, but others have suggested that a change of one standard error around the mean score is needed (around 6 or 7, depending upon the population studied). There are no studies of long term oxygen therapy to help guide us. The MIRALCE trial of biventricular pacing was powered for a 13 point improvement in MLWHF, and found a difference of 9 between treatment groups. The CARE-HF study of biventricular pacing found an improvement of 10.6 with intervention. In the absence of hard data on which to base study size, we have taken a Minnesota score of 10 as an arbitrary indicator of the minimum improvement necessary to justify the cost and inconvenience of oxygen therapy for patients.

For a 10 point difference in MLWHF score, and with a standard deviation of 25 and assuming a P of 0.025 (for two comparisons) and 80% power we will need 119 in each group or 150 in each group if we assume a 20% attrition rate.

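### The one missing-data rule adopted in section 8.2 has no stated role, and at the planned 20% attrition it turns a true 10-point MLWHF benefit into an expected 13-point apparent harm

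*Protocol*

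**What the plan says.** Section 8.2 specifies intention-to-treat analysis by ANCOVA adjusted for baseline. On missing data it states: "We will handle missing data by using the extreme values". The rule supposes the following for each absent score: "the missing value is the worst it could be for the intervention and the best it could be for the standard care group". The purpose is given as: "If there remains a statistically significant difference between treatments then one can be sure that the results are robust". Regression-based and mean imputation are mentioned only as techniques that were considered.

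Section 6.2 describes MLWHF as "a score from 0 to 105 with a higher score reflecting poorer quality of life". Read at the scale ends, a missing oxygen patient is therefore scored 105 and a missing best-medical-therapy patient 0.

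Section 8.1 sizes the trial as follows: "For a 10 point difference in MLWHF score, and with a standard deviation of 25", P of 0.025 for each of two comparisons and 80% power require "119 in each group or 150 in each group if we assume a 20% attrition rate".

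The synopsis (section 1) adds, about withdrawals, that "such incidences will be included within the quality of life analysis", without saying how.

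**The concern.** The rule moves both arms against oxygen by a large fraction of the scale, while the effect the trial seeks is only 10 points. At the planned attrition, the imputed values could decide the result.

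The sample size rests on a different analysis. Going from 119 to 150 replaces lost patients, so it treats them as absent. Section 8.2 puts them back into the analysis with opposite extreme scores.

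Two further features need attention:

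- The success criterion in section 8.2 mentions a significant difference but no direction, although the imputation can itself produce a significant difference against oxygen.
- Nothing separates a death before 12 months from any other missing score. In a population that section 8.2 itself describes as having advanced disease, and with mortality as a secondary endpoint (section 3.5), this matters. As written, the same event could be scored 0 in the control arm and 105 in an oxygen arm.

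**Working it through.** **Inputs from the protocol.** True difference 10 points, SD 25, alpha 0.025, 80% power, 119 evaluable and 150 randomised per arm, 20% attrition (all section 8.1); scale 0 to 105, higher is worse (section 6.2); 1:1:1 allocation (section 4.1).

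**Assumptions.** Two-sided tests; equal missing share m in the arms compared; a 10-point effect among observed patients; a control mean of 50 where a standard error is needed (40 to 70 also tried).

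**1. The plan's own figure.** n = 2(z₀.₉₈₇₅ + z₀.₈₀)² × 25² / 10² = 2 × (2.241 + 0.842)² × 6.25 ≈ 118.8, so 119. Then 119 / 0.8 = 148.75, so 149 against the stated 150. Both figures reproduce (a one-sided 0.025 would give 99). With 150 × 0.8 = 120 completers per arm, power is 80.4%.

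**2. Expected difference under the rule.** With control mean μ:

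- Oxygen: (1 - m)(μ - 10) + 105m
- Control: (1 - m)μ + 0 × m
- Oxygen minus control: -10(1 - m) + 105m

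The control mean cancels. At m = 0.20 the difference is -8 + 21 = **+13**, in favour of control. It is zero when 115m = 10, so at m = **8.7%**.

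**3. Power if the rule is the analysis** (150 per arm, unadjusted, control mean 50, mixture variances):

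| Missing per arm | Expected difference | Chance of significant benefit |
|---|---|---|
| 0% | -10.00 | 89% |
| 1% | -8.85 | 78% |
| 2% | -7.70 | 63% |
| 5% | -4.25 | 18% |
| 10% | +1.50 | 0.4% |
| 20% | +13.00 | below 0.00001% |

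At 20% the standard error is √((34.29² + 30.00²)/150) = 3.72. So z = 13/3.72 = 3.49, and the chance of significant apparent harm is about 89% (88% to 90% over control means of 40 to 70).

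**4. Check by simulated ANCOVA** (2,000 runs per setting, 30 of 150 missing in each arm, assumed baseline correlations 0, 0.5 and 0.7). The mean difference is 13.1, 13.0 and 12.9. No run shows significant benefit. Significant harm appears in 96%, 98% and 99.8% of runs. Completers in the same runs have 81%, 91% and 98% power for benefit. Baseline adjustment therefore does not repair the rule.

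**5. No true effect.** The expected difference at 20% missing is 105 × 0.2 = +21. With control mean 50 the arm variances are 0.8 × 3125 + 0.2 × 11025 - 61² = 984 and 0.8 × 3125 - 40² = 900. The standard error is √(1884/150) = 3.54 and z = 5.93, so significant harm is almost certain.

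**6. Break-even at 20% missing.** The true benefit δ must satisfy 0.8δ = 21, so δ = **26.25** points, over two and a half times the design effect. Any smaller benefit appears, on average, as harm.

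**7. Observed extremes instead of scale ends.** The difference becomes -8 + 0.2 × (highest - lowest). For assumed ranges of 5 to 100, 10 to 95 and 20 to 90 this gives +11, +9 and +6. The chance of significant benefit is at most about 0.002% in all three.

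**The case against.** The strongest reply is that this is a worst-case sensitivity analysis. The words *remains* and *robust* in section 8.2 presuppose a result already obtained and now being stress-tested. On that reading the main analysis uses observed scores, about 120 per arm, which keeps roughly 80% power and matches the way section 8.1 adds 20%. This stands as a possible reading, so the protocol does not support a flat statement that the stated power cannot be delivered. It does not settle the matter: the opening sentence of the rule is a general commitment, nothing labels it a sensitivity analysis, and no other handling is adopted.

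A reader might also infer that no plausible result could ever pass the check. That goes too far. With 2% missing and a true 10-point benefit, the check passes about 63% of the time unadjusted, and about 71% to 75% in ANCOVA simulations with an assumed baseline correlation of 0.5. It breaks down at the planned attrition, not at every level.

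On direction, a difference that remains is most naturally the one already found, so the protocol need not be read as counting a reversal as confirmation. The wording should still exclude it.

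On deaths, section 8.2 does not say that a death counts as a missing value, and mortality is analysed separately by Kaplan-Meier and Cox methods. It cannot be claimed that the plan intends to score deaths in this way, only that the rule as written does not prevent it.

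Finally, an unseen SAP may supply detail. But this point is about a rule that the protocol states and that sits badly with its own sample size, not about detail left out.

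**Conclusion.** The concern holds, conditionally on the role given to the rule.

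- **If primary:** it contradicts section 8.1. Power for the 10-point benefit is essentially zero at 20% attrition, and a trial of an ineffective treatment would almost always report significant harm.
- **If a robustness check:** power of the main analysis is unaffected, but the check fails at the planned attrition even when the design effect is real. It is informative only when very few scores are missing.

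The +13 points and the 8.7% crossover follow from the protocol's own figures, given scale-end values, equal attrition and a 10-point effect among observed patients. Assumed observed extremes reduce the shift to between +6 and +11 without changing its sign. With unequal attrition the control mean would no longer cancel. The power figures also depend on assumed control means and baseline correlations, but the conclusion at 20% missing does not change over the ranges tried. The direction and deaths points are gaps in wording that the same revision should close.

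**What to change.** Reword section 8.2, and the SAP to match:

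1. Name a primary handling of missing 12-month MLWHF scores that treats all three arms alike and agrees with section 8.1. Examples are ANCOVA on observed 12-month scores, or a likelihood-based repeated-measures model using the 3-, 6- and 12-month scores already scheduled in Table 1, with the 12-month contrast as the primary result.
2. State how deaths before 12 months enter the quality-of-life analysis, identically in every arm.
3. Replace the robustness criterion with a delta-adjusted or tipping-point analysis over plausible shifts, requiring the effect to stay in the same direction.
4. Keep the extreme-value calculation, if at all, only as an outer bound labelled as such.

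The cost is drafting time: no new data, visits or patients. The downside is that the primary result would rest on a missing-at-random assumption, which the tipping-point analysis is there to test.

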9.1 Definitions

Adverse Event (AE)

An adverse event (AE) is any untoward medical occurrence in a patient which does not necessarily have a causal relationship with the study treatments or procedures. An adverse event can therefore be any unfavourable and unintended sign (including an abnormal laboratory finding), symptom, or disease temporally associated with a treatment or procedure, whether or not considered related.

Adverse Reaction (AR)

All noxious and unintended responses related to a study treatment or procedure should be considered adverse drug reactions.

Serious Adverse Event (SAE)

Any untoward medical occurrence in a patient that

- (a) Results in death
- (b) Is life-threatening
- (c) Requires hospitalisation or prolongation of existing hospitalisation
- (d) Results in persistent or significant disability or incapacity
- (e) Consists of a congenital anomaly or birth defect
- (f) Is otherwise considered to be medically significant by the investigator e.g. intensive treatment in an emergency room or at home for allergic bronchospasm, blood dyscrasias or convulsions that do not result in hospitalisation.

The term "life-threatening" refers to an event in which the patient was at risk of death at the time of the event; it does not refer to an event which hypothetically might have caused death if it were more severe.

Hospitalisations planned prior to enrolment in the trial or for social reasons should not normally be considered as SAEs unless the hospitalisation has to be prolonged.

Suspected Unexpected Serious Adverse Reaction (SUSAR)

A suspected unexpected serious adverse reaction (SUSAR) is an adverse reaction that is classified as serious and it is suspected that it is caused by a study treatment or procedure.

Severity

The term severity is used to describe the intensity of an adverse event and should not be confused with seriousness which is based on the patient/event outcome or action criteria.

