Home oxygen therapy (HOT), an expensive treatment which is potentially burdensome for patients and carers, is often prescribed for patients with chronic heart failure, although it is unknown whether it is of benefit in the medium to long-term with regard to symptoms, severity of CHF, hospitalisation or survival. Also unknown, assuming oxygen is of benefit, is how it should be administered; short burst oxygen therapy (SBOT), nocturnal (NOT) or long-term (LTOT). In addition to the concern that there is no proven benefit from oxygen, some reports suggest that hyperoxia leads to clinically significant adverse haemodynamic effects such as increased vascular resistance, left ventricular filling pressure, blood pressure and reduced cardiac output due to the formation of oxygen free radicals.¹²

There are only a few, small, unpowered studies looking at the effect of short term SBOT on breathlessness and exercise tolerance in a variety of conditions. Those trials that randomised patients did not confirm benefit. A large observational study of patients with breathlessness of varying aetiology concluded that oxygen therapy was of no benefit for symptom relief in the absence of hypoxaemia, a finding echoed in a Cochrane review. A recent double blind placebo controlled study confirmed that oxygen was no better than placebo for the relief of intractable breathlessness in study participants, a few of whom had CHF.

The benefits for mortality and morbidity of LTOT in patients with chronic obstructive pulmonary disease and hypoxia are well established,¹⁷ but dependent upon good compliance. One study has suggested that there is less than 30% compliance with prescribed therapy.¹⁸ LTOT (>15 hours per day) has not been studied in patients with left ventricular dysfunction or CHF. The criteria which should be used to assess suitability of LTOT in patients with CHF, let alone benefit in terms of survival, severity of disease or symptomatology is unknown. It is also unknown whether CHF patients would tolerate the intervention which would be more intrusive than NOT alone.

NOT has been studied in small randomised trials in patients with CHF with a maximum follow-up of 3 months¹⁹ ²⁰ ²¹ ²² ²³ and appears to reduce CSA and nocturnal sympathetic activity; evidence of improvement either of cardiac function or symptoms is inconsistent.

3. Aims and Objectives

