9.2 Adverse Event (AE) Reporting

An adverse event (AE) is any untoward medical occurrence in a patient who is taking part in a research study. In this trial, a pre-existing condition (i.e., a disorder present before the AE reporting period started and noted on the pre-treatment medical history/physical examination form/medical notes) is not to be reported as an AE unless the condition worsens or episodes increase in frequency during the AE-reporting period.

Diagnostic and therapeutic non-invasive and invasive procedures, such as surgery, are not to be reported as AEs. However, the medical condition for which the procedure is performed is to be reported if it meets the definition of an AE. For example, an acute appendicitis that begins during the AE reporting period is to be reported as the AE (serious) and the resulting appendicectomy noted under comments.

If a clinically significant abnormal laboratory value occurs, this abnormality (but not the value itself) should be entered on the adverse event page.

Expected Adverse events include the following:

- Worsening of symptoms of heart failure
- Admission to hospital for acute decompensation of heart failure
- Worsening angina
- Admission to hospital with angina

Each trial subject will be questioned about adverse events at each visit. The investigator will record all directly observed AEs and all AEs spontaneously reported by the trial subject.

The AE reporting period for this trial begins on randomisation, and ends 30 days after the patients' final research clinic appointment.

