9.3 Recording and Reporting Instructions

Each AE will be classified by the investigator as SERIOUS or NONSERIOUS and should be recorded on the 'serious adverse event form' or 'non serious adverse event form'.

An adverse event is defined as being serious if it is an untoward occurrence that:

- (a) results in death,
- (b) is life-threatening,
- (c) requires hospitalisation or prolongation of existing hospitalisation,
- (d) results in persistent or significant disability or incapacity.
- (e) consists of a congenital anomaly or birth defect, or
- (f) is otherwise considered medically significant by the investigator

If a research participant experiences an adverse event which in the opinion of the chief investigator is both

- 'related': that is, it resulted from administration of any of the research procedures;
 and
- 'unexpected': that is, the type of event is not listed in the protocol as an expected occurrence.

Then it will be reported to the Research Ethics Committee that gave a favourable opinion of the study and the sponsor (Hull and East Yorkshire Hospitals NHS Trust R&D department) within 15 days of the CI becoming aware of the event using the NRES safety report form available from:

http://www.nres.npsa.nhs.uk/applications/after-ethical-review/safetyreports/safety-reports-for-all-other-research/#safetynonCTIMPrepotingSAEs

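### The SUSAR definition in 9.1 omits expectedness and disagrees with the reporting rule in 9.3, so a serious heart-failure or angina event judged caused by oxygen gets no individual 15-day report to the ethics committee and sponsor

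*Protocol*

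**What the plan says.** Section 9.1 of the protocol spells out the SUSAR acronym in full, then defines it as an "adverse reaction that is classified as serious and it is suspected that it is caused by a study treatment or procedure". Seriousness and suspected causation are the only two tests.

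Section 9.3 sets the rule for individual expedited reporting. The chief investigator must judge the event to meet two conditions:

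- The first is worded as "related': that is, it resulted from administration of any of the research procedures".
- The second, unexpectedness, means that "the type of event is not listed in the protocol as an expected occurrence".

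If both are met, "Then it will be reported to the Research Ethics Committee that gave a favourable opinion of the study and the sponsor", within 15 days of the chief investigator becoming aware.

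The list that 9.3 relies on is in section 9.2. It has four entries. Two are "Worsening of symptoms of heart failure" and "Admission to hospital for acute decompensation of heart failure"; the other two are worsening angina and hospital admission with angina. The list makes no distinction by cause.

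In section 2 (Background and Rationale) the protocol states that "some reports suggest that hyperoxia leads to clinically significant adverse haemodynamic effects", and gives raised left ventricular filling pressure and lower cardiac output among the examples.

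**The concern.** The two sections that decide what is escalated use different tests, and they part company on the events most common in this population. An event that 9.1 calls a SUSAR can fall outside the only paragraph that sets a recipient and a deadline for individual reporting.

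The definition is also applied in practice. Section 10.1 has the chief investigator say promptly whether each SAE is a SUSAR, and gives the trials unit the reporting of both SAEs and SUSARs. Two people working from different pages could classify and route the same admission differently.

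The stake is prompt notice to the ethics committee and sponsor of a suspected treatment harm. Decompensation is plainly expected from severe heart failure. Nothing in the protocol presents it as an accepted reaction to oxygen, and section 2 says long-term oxygen has not been studied in left ventricular dysfunction or heart failure. Yet the 9.2 list removes the reporting consequence even when an investigator has attributed the event to oxygen. The haemodynamic effects cited in section 2 are ones for which decompensation would be a plausible clinical expression.

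**Working it through.** No formula applies and the protocol gives no figure to reproduce. The check is to put the same test events through 9.1 and 9.3.

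**Criteria side by side**

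| Criterion | 9.1 (SUSAR) | 9.3 (15-day report) |
|---|---|---|
| Serious | required | not repeated in the two conditions |
| Related | to a study treatment or procedure | to research procedures only |
| Unexpected | not required | required: type not on the 9.2 list |

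**Test events**

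| Event | SUSAR under 9.1? | 15-day report under 9.3? | Agree? |
|---|---|---|---|
| A. Admission for decompensated heart failure, judged caused by oxygen | Yes: serious through hospitalisation, suspected related | No: type is listed in 9.2 | No |
| B. Serious, related event of an unlisted type | Yes | Yes | Yes |
| C. Non-serious, related event of an unlisted type | No | Yes, on the literal words | No |

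Events B and C assume that harm from the oxygen itself counts as resulting from research procedures. The 9.3 wording leaves that open.

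Events A and C together give an odd ordering. Read literally, a minor related event of an unlisted type gets the 15-day report, and a hospital admission attributed to oxygen does not.

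**Which listed events are affected.** The two admission entries are serious by definition, because hospitalisation is a seriousness criterion. The two worsening entries are affected only when the event meets a seriousness criterion in some other way.

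**Where event A still appears**

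- Section 9.3: it is entered on a serious adverse event form.
- Section 10.1: the chief investigator assesses it, and it falls within the trials unit's SAE reporting duty, for which that section names no recipient or deadline.
- Section 10.4: adverse events are logged continuously as a key indicator for the TSC and DMEC.
- Section 10.2: the DMEC may review any SAE.

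What event A lacks is the individual 15-day report to the ethics committee and sponsor.

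**Patients exposed.** Randomisation is 1:1:1 with 450 patients, so 450 × 2/3 = 300 are allocated to oxygen. The trial is open label, so attributing an event to oxygen is possible in practice. The protocol gives no rate of related decompensation, so an expected number of affected reports cannot be derived.

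**The case against.** The strongest reply is that the practical gap is narrow. Every event has its own form, SAEs are assessed, and the DMEC sees them. Section 9.3 does not use the term SUSAR and 9.1 attaches no deadline to it, so the loose definition mainly widens the set of events that the chief investigator and DMEC consider. Simply inserting the missing word in 9.1 would narrow that set and confirm the exclusion of event A. Section 9.2 also does not say what the listed events are expected from, so reading the list as disease-related is an interpretation. All of this stands. It limits the size of the point and shapes the fix, but it does not remove the conflict.

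Four stronger readings are tempting, and the protocol does not support them.

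- A reader might infer that such events are never reported individually, or have no route at all to the sponsor. Sections 9.3, 10.1, 10.2 and 10.4 show otherwise; only the 15-day report is missing. A related death is also not clearly one of the four listed types, so 9.3 may still capture it.
- A reader might infer that the protocol names worsening heart failure as a harm of oxygen. Section 2 attributes haemodynamic effects to some reports. The step to decompensation is a plausible inference, and section 2 draws no link to angina.
- A reader might set the 15 days against the usual 6-month DMEC interval and call the difference a delay in detection. The first is a reporting deadline that runs from awareness and the second is a meeting schedule. An event already judged related has already been detected.
- A reader might infer that the DMEC will not compare events by arm. Its terms do not exclude this, and such tables are commonly left to a charter or analysis plan.

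**Conclusion.** The point holds as an internal contradiction with a practical consequence. Sections 9.1 and 9.3 disagree on expectedness, on seriousness and on what an event must be related to. As a result, a serious event of a listed type that is judged caused by oxygen is a SUSAR under 9.1 but gets no individual 15-day report under 9.3.

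The effect is confined to serious events of the four listed types that are attributed to treatment in the two oxygen arms. It concerns which suspected harms reach the ethics committee and sponsor promptly. No endpoint, sample size or analysis depends on it.

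The conclusion rests on reading 9.2 and 9.3 as written: the type of event alone decides expectedness, and no other rule in the protocol overrides this. Its importance rests on the clinical inference from section 2 that decompensation could be how the cited haemodynamic effects show themselves. It should be corrected.

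**What to change.** Make two changes together.

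1. **Align 9.1 and 9.3.** Add unexpected to the SUSAR definition in 9.1. State in 9.3 that the 15-day rule concerns serious events, and use the same object of relatedness in both sections, covering study treatment as well as procedures.
2. **State what the list means.** In 9.2, with a cross-reference in 9.3, say that the four entries are events expected from the underlying disease. A serious event of a listed type that is judged related to oxygen then counts as unexpected for reporting and follows the 15-day route.

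The first change alone would settle the wording but confirm that these events stay outside the 15-day report, so the second is needed. The sponsor should confirm that the list was meant in this sense.

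The cost is a few sentences in 9.1 to 9.3 and a few extra individual reports. No data collection or analysis changes.
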